6. STUDY DRUG

Extent of exposure to study drug will be examined by assessing the total duration of exposure to study drug and the level of adherence relative to the study drug regimen specified in the protocol.

6.1. Duration of Exposure to Study Drug

Total duration of exposure to study drug will be defined as following and will be expressed in days.

Duration of exposure to study drug = (last dose time - first dose time)/24 hour.

The total duration of exposure to study drug will be summarized using descriptive statistics and using the number and percentage of subjects exposed through the following time periods: 1 day, 2 days,, 14 days. Summaries will be provided by treatment group for the Safety Population

6.2. Adherence to Study Drug

The total number of doses administered and missed dose or dose interruption in clinical database will be summarized using descriptive statistics.

6.2.1. On-Treatment Adherence

The level of treatment period adherence to an investigational drug dosing regimen depends on the percentage of the total amount of investigational drug received by the subject relative to the total amount of investigational drug expected to be used under the investigational drug regimen during the subject's actual treatment period.

The total number of infusions of study drug and the total number of infusions of study drug expected to be used during the subject's actual treatment according to the study drug regimen will take into account the data in the EDC.

The level of adherence during the treatment period is expressed as a percentage and is calculated according to the following formula:

$$\text{On-Treatment Adherence (\%)} = \frac{\text{Total Number of Study Drug Doses Administered}}{\text{The total number of infusions of the study drug expected to be used according to the study drug regimen during the subject's actual treatment}} \times 100$$

Descriptive statistics for the level of on-treatment adherence with the number and percentage of subjects belonging to adherence categories (< 80%, ≥ 80 to $< 90\%$, $\geq 90\%$) will be provided by treatment group for the Safety Population.

A by-subject listing of study drug administration will be provided by subject ID number (in ascending order) and visit (in chronological order).

7. CONCOMITANT MEDICATIONS (ANTIBACTERIALS AND OTHERS) AND DIAGNOSTIC/THERAPEUTIC PROCEDURES

Concomitant medications (antibacterials and others) will be coded using the current version of the World Health Organization (WHO) Drug dictionary.

7.1. Combined Use of Non-Study Drugs (Antimicrobials and other Drugs)

Concomitant medications (antibacterials and others) are defined as medications taken while a subject took study drug. The definition of systemic gram-negative antibacterials is detailed in Section 5.5.

Use of concomitant medications will be summarized by Anatomical Therapeutic Chemical (ATC) drug class Level 2 and preferred name using the number and percentage of subjects for antibacterials and others separately. A subject reporting the same medication more than once will be counted only once when calculating the number and percentage of subjects who received that medication. The summary will be ordered by ATC medical class and preferred term in descending overall frequency. For drugs with the same frequency, sorting will be done alphabetically.

For the purposes of analysis, any medications with a start date prior to or on the first dosing date of study drug and continued to be taken after the first dosing date, or started after the first dosing date but prior to or on the last dosing date of study drug will be considered concomitant medications. Medications started and stopped on the same day/time as the first dosing date/time or the last dosing date/time of study drug will also be considered concomitant. Medications with a stop date/time prior to the date/time of first dosing date/time of study drug or a start date/time after the last dosing date/time of study drug will be excluded from the concomitant medication summary. If a partial stop date/time is entered, any medication with the month and year (if day is missing) or year (if day and month are missing) prior to the date of first study drug administration will be excluded from the concomitant medication summary. If a partial start date is entered, any medication with the month and year (if day is missing) or year (if day and month are missing) after the study drug stop date will be excluded from the concomitant medication summary. Medications with completely missing start and stop dates will be included in the concomitant medication summary, unless otherwise specified.

Summaries will be based on the Safety Population.

All concomitant medications (antibacterial and others) will be provided in a by-subject listing sorted by administration date in chronological order.

7.2. Treatment History (Non-Pharmacological)

Treatment history, i.e., diagnostic/therapeutic manipulation of combined non-pharmacological treatments will be summarized by System Organ Classification (SOC) and preferred terminology, and percentages will be calculated using the number of subjects in each

treatment group. When calculating the number of subjects and percentages, subjects reporting the same diagnostic/therapeutic maneuver multiple times will be counted only once. The summary table will be sorted in descending order of total frequency of SOC and preferred terms. For diagnostic/therapeutic operations with the same frequency, they will be sorted alphabetically.

Summaries will be based on the Safety Population.

All concomitant diagnostic/therapeutic procedures will be provided in a by-subject listing sorted by administration date in chronological order.

8. EFFICACY ANALYSIS

8.1. Primary Efficacy Endpoint

The primary endpoint is the Day 14 all-cause mortality rate in the MITT population.

8.1.1. Estimand for Primary Endpoint

8.1.1.1. Treatment

IMI-XNW4107 or IMI/REL given as IV infusions for a recommended treatment duration of 7 to 14 days.

8.1.1.2. Population

All subjects who underwent randomization and received at least 1 dose of study drug (MITT population).

8.1.1.3. Variable

Day 14 all-cause mortality rate after randomization.

8.1.1.4. Intercurrent Events and Handling Strategies

- Premature discontinuation of study treatment: based on treatment policy strategy, data after occurrence of intercurrent events will still be included in the analysis.
- Usage of rescue antibiotics: based on treatment policy strategy, data after occurrence of intercurrent events will still be included in the analysis.

8.1.1.5. Population-level Summary

Difference in Day 14 all-cause mortality rate after randomization between treatment groups (IMI-XNW4107 - IMI/REL).

8.1.2. Analysis Methods for Primary Estimand

8.1.2.1. Primary Efficacy Analysis

In order to determine whether IMI-XNW4107 is non-inferior to IMI/REL in subjects with HABP/VABP, a non-inferiority margin of 10% will be used, the study hypothesis to demonstrate noninferiority of IMI-XNW4107 to IMI/REL on all-cause mortality rate at Day 14 can be written as follows:

$$\text{Null Hypothesis} \quad H_0: p_1 - p_2 > 10\%$$

$$\text{Alternative Hypothesis} \quad H_1: p_1 - p_2 \leq 10\%$$

Where p_1 is the all-cause mortality rate for IMI-XNW4107 and p_2 is the all-cause mortality rate for IMI/REL.

Subjects with unknown survival status by Day 14 will not be considered as deaths for both treatment group.

The non-inferiority assessment will be based on the two-sided CI for the difference in proportions (IMI-XNW4107 minus IMI/REL). Stratified proportion difference along with its two-sided 95% CI using stratum-adjusted Mantel-Haenszel (MH) approach (Koch, 1989) stratified by

randomization stratification factors for treatment comparison (IMI XNW4107 group minus IMI/REL group) will be provided.

The stratified point estimates for the difference in proportions of subjects' all-cause mortality rate at Day 14 between IMI-XNW4107 group and IMI/REL group will be calculated using the following formula:

$$\hat{p}_1 - \hat{p}_2 = \frac{\sum W_h d_h}{\sum W_h}$$

Where $d_h = \hat{p}_{1h} - \hat{p}_{2h}$ is the difference in the proportion of subjects' all-cause mortality rate between IMI-XNW4107 group and IMI/REL group in stratum h ($h = 1, 2, \dots, K$), and $W_h = \frac{n_{1h}n_{2h}}{n_{1h} + n_{2h}}$ is the weight based on the harmonic mean of sample size per treatment group for each stratum where n_{1h} and n_{2h} are the sample size of the IMI-XNW4107 group and IMI/REL group in stratum h , respectively.

The 95% stratum-adjusted MH CIs will be calculated using the following formula:

$$\hat{p}_1 - \hat{p}_2 \pm Z_{1-\alpha/2} \cdot SE(\hat{p}_1 - \hat{p}_2)$$
$$\text{Where } SE(\hat{p}_1 - \hat{p}_2) = \sqrt{\sum W_h^2 \left(\frac{\hat{p}_{1h}^*(1-\hat{p}_{1h}^*)}{n_{1h}-1} + \frac{\hat{p}_{2h}^*(1-\hat{p}_{2h}^*)}{n_{2h}-1} \right)}$$

Where $SE(\hat{p}_1 - \hat{p}_2)$ = $\sqrt{\sum W_h^2 \left(\frac{\hat{p}_{1h}^*(1-\hat{p}_{1h}^*)}{n_{1h}-1} + \frac{\hat{p}_{2h}^*(1-\hat{p}_{2h}^*)}{n_{2h}-1} \right)}$, $\hat{p}_{1h}^* = \frac{m_{1h}+0.5}{n_{1h}+1}$, $\hat{p}_{2h}^* = \frac{m_{2h}+0.5}{n_{2h}+1}$, and m_{1h} and m_{2h} are the number of subjects who experience all-cause mortality from the IMI-XNW4107 group and IMI/REL group in stratum h , respectively. $Z_{(1-\alpha/2)}$ is the 97.5% percentile of normal distribution with $\alpha = 0.05$.

Non-inferiority will be concluded if the upper limit of the two-sided 95% CI is less than or equal to 10%. If non-inferiority is demonstrated, a test for superiority will be performed, and superiority will be concluded if the upper limit of two-sided 95% CI is less than 0

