1.2. Study Design

This is a prospective, multicenter, double-blind, randomized, active-controlled study to evaluate the efficacy, safety, and tolerability of IMI-XNW4107 in comparison with IMI/REL in the treatment of adults with HABP/VABP caused by Gram-negative bacteria.

Approximately 450 subjects with a clinical diagnosis of HABP/VABP who meet all eligibility criteria, and assessed by the investigator as requiring 7 to 14 days of IV antibiotic treatment in the hospital will be randomized.

Randomization will be stratified by type of infection (non-ventilated HABP vs. ventilated HABP/VABP), Acute Physiology and Chronic Health Evaluation II (APACHE II) score (<15 vs. ≥ 15), and country/region (China vs. Rest of World). At least 50% of enrolled subjects will be on mechanical ventilation at enrollment (VABP/ventilated HABP).

Subjects will be randomly assigned to study treatment in a double-blind manner in a 2:1 ratio via an Interactive Web/Voice Response System (IXRS) to receive either imipenem 500 mg/cilastatin 500 mg-XNW4107 250 mg (N=300) infused IV as a 30-minute infusion (± 5 minutes) q6h (± 30 minutes) or IMI/REL 1.25 g (imipenem 500 mg/cilastatin 500 mg/relebactam 250 mg) (N=150) infused IV as a 30-minute infusion (± 5 minutes) q6h (± 30 minutes) for a recommended treatment duration of 7 to 14 days (judged by the investigator).

Dose adjustments will be required for subjects with abnormal renal function.

Concomitant treatment with optional linezolid (600 mg as an IV infusion over 30 to 120 minutes every 12 hours) as judged by the investigator can be given to subjects in both arms to provide coverage for methicillin-resistant *Staphylococcus aureus* (MRSA) as per local standard of care. The treatment duration of MRSA will be determined by the investigator. The recommended treatment duration for a confirmed MRSA infection is a minimum of 7 days, with a minimum of 14 days for MRSA bacteremia. Empiric linezolid treatment will be stopped if the final culture results from the baseline lower respiratory tract sample do not demonstrate the presence of MRSA. For subjects in whom linezolid cannot be used, IV vancomycin may be used.

In addition to all-cause mortality (survival) through Day 14 (primary endpoint) and through Day 28, assessments of clinical and microbiological outcomes will be performed at Day 4 (clinical outcome only), EOT (the last day of study treatment [+1 day]), TOC (Day 21 [± 2 days]), and an LFU visit (Day 28 [± 3 days]).

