1.3. Sample Size and Test Efficacy

Assuming an all-cause mortality rate of 10% for both treatment groups, a 2:1 randomization ratio, and a one-sided significance level of 0.025, a trial of 450 subjects will have more than 90% power to show non-inferiority with a 10% non-inferiority margin.

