8.2.1.1. All-Cause Mortality Rate Analysis

Day 14 and Day 28 all-cause mortality were analyzed in the different populations defined in Section 8.2 in a manner similar to the primary efficacy endpoints described in Section 8.1.2.1.

Provides a list of all-cause mortality rates for subjects at Day 14 and Day 28, in ascending order of subject number.

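### The standard error in SAP 8.1.2.1 is not divided by the sum of the stratum weights, so as written the primary confidence interval is about 100 times too wide and the 10% margin cannot be met

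*SAP*

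**What the plan says.** SAP 8.1.2.1 sets out the primary analysis in four steps.

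- Each stratum h has the weight "W_h = \frac{n_{1h}n_{2h}}{n_{1h} + n_{2h", that is, the product of the two arm sizes over their total.
- The point estimate is the sum of weight times stratum difference, divided by the sum of the weights.
- The standard error of that estimate is the square root of the sum over strata of "W_h^2 \left(\frac{\hat{p}_{1h}^*(1-\hat{p}_{1h}^*)}{n_{1h}-1} + \frac{\hat{p}_{2h}^*(1-\hat{p}_{2h}^*)}{n_{2h}-1". The starred proportions are `(m + 0.5)/(n + 1)`, where m is the number of deaths. Nothing divides the root.
- The interval is the estimate plus or minus the normal quantile times this standard error, with no further scaling. Non-inferiority needs an upper limit of at most 10%; superiority needs an upper limit below 0.

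SAP section 11 drops country/region from the stratification. That leaves infection type by APACHE II category, or four strata. Day 14 and Day 28 mortality in the other populations are analysed "in a manner similar to the primary efficacy endpoints described in Section 8.1.2.1". SAP 8.1.2.2 (multiple imputation), 8.2.2.1 (clinical), 8.2.3.3 (microbiological) and 8.2.4.1 (overall) also refer back to this method.

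**The concern.** The estimate and its standard error are on different scales. If the estimate is `Σ W_h d_h / Σ W_h`, its variance is `Σ W_h² Var(d_h) / (Σ W_h)²`. The SAP gives only the numerator, which is the variance of `Σ W_h d_h`. That would be correct only if the weights summed to 1, and weights of the form `n1h n2h/(n1h + n2h)` do not.

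Both the non-inferiority and the superiority decision are read from the upper limit of this interval. The SAP spells the formula out down to the 0.5 adjustment, so a programmer or an independent validator could reasonably code it as printed. If the program instead uses a correct formula, the primary analysis departs from its written specification.

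**Working it through.** **Inputs.** SAP 1.2 plans 300 subjects on the test drug and 150 on the comparator. The planning case in SAP 1.3 is 10% mortality in each arm, 2:1 allocation and a 10% margin. For that case it states: "a one-sided significance level of 0.025, a trial of 450 subjects will have more than 90% power". The split across the four strata is not given. I assume equal strata (75 versus 37.5 in each) and vary this below.

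**The plan's own figure.** The planning standard error is `sqrt(0.1×0.9/300 + 0.1×0.9/150) = sqrt(0.0003 + 0.0006) = 0.030`. Power is `Φ(0.10/0.030 − 1.96) = 91.5%`, so the claim of more than 90% is reproduced. A correct stratified standard error should therefore be near 0.03.

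**Sum of the weights.** Each stratum has `W_h = 75×37.5/112.5 = 25`, so `Σ W_h = 100`. This equals 300×150/450, and it is the same for any number of strata with 2:1 allocation in each.

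**Standard error with 10% mortality in both arms.**

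- Test arm, per stratum: `p* = (7.5 + 0.5)/76 = 0.1053`; `p*(1 − p*)/74 = 0.001273`
- Comparator, per stratum: `p* = (3.75 + 0.5)/38.5 = 0.1104`; `p*(1 − p*)/36.5 = 0.002690`
- Sum per stratum: 0.003963
- As written: `sqrt(4 × 25² × 0.003963) = 3.15`
- Divided by `Σ W_h`: `3.15/100 = 0.0315`, in line with the planning value of 0.030

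| | As written | Divided by Σ W_h |
|---|---|---|
| Standard error | 3.15 | 0.0315 |
| 95% half-width | 617 points | 6.2 points |
| Upper limit (difference 0) | 617% | 6.2% |
| Meets the 10% margin | no | yes |

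Whole-number strata (75/37, 75/38, 75/37, 75/38 with deaths 7, 8, 7, 8 versus 4, 4, 4, 3) give the same result: 3.147 as written and 0.0315 corrected.

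**Other layouts, 10% mortality, formula as written.**

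| Layout | Σ W_h | Upper limit as written | Corrected |
|---|---|---|---|
| 1 stratum | 100 | 595% | 6.0% |
| 8 equal strata (region kept) | 100 | 645% | 6.5% |
| 4 unequal strata (illustrative) | 100 | 600% | 6.0% |
| 270 versus 180 (illustrative mix of 1:1 and 2:1) | 108 | 637% | 5.9% |
| 225 versus 225 | 112.5 | 648% | 5.8% |
| 887 subjects, 2:1 (largest in Table 2.2-1) | 197 | 846% | 4.3% |

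**Can any outcome meet the margin?** With no deaths in either arm and four equal strata, the upper limit as written is 205%. The most favourable outcome possible is 0% mortality on test and 100% on comparator: the difference is at its minimum of −1, and each stratum variance is also at its minimum because every proportion is at an extreme. The standard error as written is then 1.048 and the upper limit is `−1 + 1.96 × 1.048 = 1.05`, or 105%. With four equal strata at the planned size, therefore, no data set can meet a 10% limit.

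**The case against.** The strongest objection is that the text was machine-read from PDF and a denominator may have been lost. The expression is printed twice in succession in 8.1.2.1, which looks like one source line read twice, so the repetition adds no evidence. Other parts of the SAP, such as Table 2.2-1, are visibly damaged. This cannot be ruled out. However, the fraction for the point estimate, the fraction for the weight and the nested fractions inside the root all came through intact. The protocol's primary analysis section is redacted and cannot settle it. A look at the source PDF will.

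Second, the SAP names the stratum-adjusted Mantel-Haenszel approach with a reference, so the intended calculation is clear. A program built on that method would probably normalise, and an upper limit above 100% would be noticed at once. The printed error also works against the sponsor, since it cannot create a false claim of non-inferiority. All of this stands. It lowers the practical risk but does not make the written formula correct.

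Third, not every interval is affected. The subgroup risk differences (8.1.2.4) are unstratified, and the hazard ratio in 8.1.2.2 comes from a Cox model. There is also one degenerate exception: a single stratum with 0% versus 100% mortality gives an upper limit of 3.1%. That is not the planned four-stratum analysis.

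**Conclusion.** The formula is wrong as written, and the SAP's own lines show it: the estimate is divided by the sum of the weights and its standard error is not. The inflation factor is exactly `Σ W_h`: 100 at 300 versus 150, up to 112.5 for 450 subjects if all allocation were 1:1, and 115 to 197 if the total were raised to between 518 and 887 at 2:1. These values assume the same allocation ratio in every stratum. The actual strata, and the numbers randomised at 1:1 and at 2:1, are not in the documents, but no layout tried changes the conclusion.

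The consequence depends on the formula being applied literally. The sample size and power statements do not use it and are unaffected. Because it governs the primary decision, it must be corrected in the SAP.

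**What to change.** Check the expression in 8.1.2.1 against the source PDF. If the divisor is absent there, replace it with

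`SE = sqrt( Σ W_h² [ p1h*(1 − p1h*)/(n1h − 1) + p2h*(1 − p2h*)/(n2h − 1) ] ) / Σ W_h`

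or, equivalently, divide by `(Σ W_h)²` under the root. Confirm that the primary analysis program and its independent check use the corrected form, and that the analyses referring back to 8.1.2.1 inherit it. Record the correction in the SAP revision table before unblinding, or in the study report if the SAP is already final.

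The cost is a one-line correction and a program check. It changes neither the design, the margin, the sample size nor the point estimate.

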8.1.2.2. Sensitivity Analysis

In the primary analysis, for both treatment groups, subjects with unknown survival at Day 14 will be considered missing. To evaluate the impact of missing data on all-cause mortality at Day 14, the following multiple fill method will be used:

Considering that within the same treatment group, within the same randomization stratification, subjects with unknown survival at day 14 and subjects with no deletions have similar outcomes, the data from all observed subjects with unknown survival at day 14 will be used to fill in subjects with unknown survival at day 14 in a multiple imputation method. A logistic regression model (logistic regression) will be used to generate the post-fill dataset, and the following covariates will be included in the model: treatment group (test drug vs. control drug), type of infection (non-ventilated HABP vs. ventilated HABP), and APACHE II scores (continuous variable). Newly generated datasets after filling were analyzed using the same methods as

described in Section 8.1.2.1. The results of these analyses were then finally combined using Rubin's Rule (Rubin's Rule) to derive the difference in proportions of the IMI-XNW4107 group minus the IMI/REL group and their two-sided 95% confidence intervals.

For the MITT population, the p-value from the stratified log-rank test comparing the IMI-XNW4107 group and the IMI/REL group will be provided, accompanied by Kaplan-Meier curves; the hazard ratio and its 95% confidence interval between the IMI-XNW4107 group and IMI/REL group will be calculated using a stratified Cox regression model.

8.1.2.3. Supplementary Analysis

For the results of the primary effectiveness analyses (both for subjects enrolled in China and outside of China), as well as the analyses described above for subjects enrolled in China, bar charts of Day 14 all-cause mortality by treatment group will be provided, along with estimated stratified proportional differences and their two-sided 95% CIs.

8.1.2.4. Subgroup Analysis

Day 14 all-cause mortality will be analyzed in the MITT population for the following subgroups

- Age (< 65 and \geq 65)
- Gender (male and female)
- Country/region (China and the rest of the world)
- Type of infection at baseline (non-ventilated HABP and ventilated HABP)
- Baseline APACHE II scores (<15 and \geq 15)
- ICU admission at baseline (yes/no)
- Baseline eGRF classification (<30 mL/min, 30 to <60 mL/min, 60 to <90 mL/min, 90 to <150 mL/min, 150 to <250 mL/min and \geq 250 mL/min)
- Baseline liver function (normal, abnormal)
- Received antimicrobial therapy for this HABP/VABP (yes/no)
- Whether the subject's prior antibiotic therapy was considered a clinical treatment failure (yes/no)
- Baseline lower respiratory tract gram-negative infections (mono/poly)

- Top 5 Ranking of Respiratory Gram-Negative Bacteria under Baseline HABP/VABP (5 most frequent in combined dose groups)
- Resistance to gram-negative pathogenic bacteria of the respiratory tract at baseline (carbapenem-resistant/non-resistant)
- Concomitant bacteremia at baseline (yes/no)

For a subject, if the value of the grouping variable cannot be determined, this subject will be excluded from the corresponding subgroup analysis. Non-stratified risk difference between treatment groups will be evaluated for each of the subgroups. A forest plot will graphically present the non-stratified risk difference and 95% CI using normal approximation with a continuity correction on the treatment differences in the all-cause mortality rates at Day 14 between IMI-XNW4107 and IMI/REL for each of the subgroups. For both treatment groups, subjects with unknown survival at Day 14 will not be considered dead.

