11. CHANGES FROM PROTOCOL-SPECIFIED ANALYSIS

Subjects will be randomly assigned to treatment groups in a 1:1 ratio (Protocol V1.0) and a 2:1 ratio (Protocol V3.3 and beyond) using stratified randomization via interactive voice or web-based response systems (IRT). In the final analysis, the data will contain subjects enrolled in both randomized ratios.

In the protocol, for the primary efficacy endpoint, the randomization stratification factor-corrected Mantel-Haenszel stratification method (Koch, 1989) will be used to provide the difference in proportions between groups (i.e., rate difference: IMI-XNW4107 group minus IMI/REL group) and their 95% two-sided CIs. However, due to the number of subjects actually enrolled in other countries and regions outside of China was very small, in Section 8.1.2.1, country/region (China vs. other countries and regions) in the randomization stratification factor was excluded from the analysis, and treatment comparisons were made by the following stratification factor (IMI XNW4107 group minus IMI/REL group):

- Type of infection (non-ventilated HABP vs. ventilated HABP).
- APACHE II scores (<15 versus ≥ 15).

New extended micro-MITT 2 analysis population and addition of microbial efficacy by subject and microbial efficacy by pathogen in the extended micro-MITT 2 population.

For imputation rules of all-cause mortality (except for sensitivity analyses), subjects with unknown survival status at Day 14 and Day 28 will not be considered deaths in either treatment group.

[figure not shown]
[figure not shown]
[figure not shown]
[figure not shown]
[figure not shown]
[figure not shown]
[figure not shown]
[figure not shown]
[figure not shown]
[figure not shown]

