14. SAP VERSION REVISIONS

Revision date	Section	Summary of Revisions	Reason for Revision
June 25, 2025	Department of Biostatistics	
 1. Update abbreviations. 2. Revise descriptions in the Microbiology Data section. 3. For all-cause mortality imputation (excluding sensitivity analyses), Subjects with unknown survival status at Day 14/Day 28 shall not be considered deaths in either treatment group. Survival analysis has been added. 4. Any pathogen detected in blood culture samples is defined as bacteremia. 5. For pathogens missing IMI/REL susceptibility data, impute using IMI susceptibility results. 6. In primary Estimand, APACHE II score is used as a continuous variable in the sensitivity analysis. 	
 1. Added new abbreviations. 2. Added detailed descriptions. 3.  4.  5.  6.  7.  8.  9.  10.  11.  12.  13.  
subjects with missing survival status will not be considered deaths. Results of the survival analysis were also supplemented.
 
4. The definition of bacteremia was updated based on expert judgment.
 
5. The mechanism of action of imipenem/relebactam (IMI/REL) is that relebactam inhibits bacterial β-lactamases, thereby restoring activity against imipenem-resistant pathogens. For pathogens inherently susceptible to imipenem, relebactam is not required. Therefore, for imipenem-susceptible pathogens missing IMI/REL susceptibility data, susceptibility to IMI/REL shall be imputed as susceptible (S).
 
6. All-cause mortality in the trial was low, and some strata at randomization contained no deceased subjects; these data could not be used for imputation.

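### The subgroup forest plot's corrected normal-approximation interval is too narrow when one or both arms have no deaths (minor; descriptive display only)

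*SAP*

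**What the plan says.** SAP 8.1.2.4 lists 14 subgroup factors for Day 14 mortality in the MITT population (35 levels by my count). "Non-stratified risk difference between treatment groups will be evaluated for each of the subgroups", and the forest plot shows a "95% CI using normal approximation with a continuity correction on the treatment differences in the all-cause mortality rates at Day 14". The section gives no formula for the correction, no minimum subgroup size or death count, and no rule for an arm without deaths.

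Two other places bear on how sparse the rows may be. SAP 14 explains a change to the imputation model by noting that "All-cause mortality in the trial was low, and some strata at randomization contained no deceased subjects". SAP 11 drops region from the primary stratification because "the number of subjects actually enrolled in other countries and regions outside of China was very small", yet Rest of World remains a subgroup row.

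The primary analysis has some protection: the standard error in SAP 8.1.2.1 uses (m+0.5)/(n+1) for each stratum proportion, so it never reaches zero. Section 8.1.2.4 does not mention that device. SAP 8.2.1.2, 8.2.2.2, 8.2.3.4 and 8.2.4.2 refer back to 8.1.2.4 for Day 28 mortality and for clinical, microbiological and overall success.

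**The concern.** The normal-approximation variance is p1(1−p1)/n1 + p2(1−p2)/n2. An arm with no deaths contributes nothing to it, although zero out of 10 or 20 is weak evidence about the true rate. If both arms have no deaths, the whole variance disappears and the bar is just the continuity term.

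Readers of a forest plot take bar length as precision. Here some of the least informative rows could carry some of the shortest bars. The stake is a misleading display, in a trial whose own SAP reports low mortality.

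**Working it through.** **Inputs.** From SAP 1.3: "Assuming an all-cause mortality rate of 10% for both treatment groups", a "one-sided significance level of 0.025" and the claim that "a trial of 450 subjects will have more than 90% power to show non-inferiority with a 10% non-inferiority margin". Allocation is 2:1, 300 v 150 (SAP 1.2). Subgroup sizes and deaths are not given; I assume 2:1 subgroups of 20/10, 40/20 and larger (test/control), with mortality between 2% and 15%.

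**The plan's own figure.** At 300/150 and 10% in both arms, SE = √(0.09/300 + 0.09/150) = 0.030. Power = Φ(0.10/0.030 − 1.96) = Φ(1.37) = 91.5%, which agrees with the stated figure. The normal approximation raises no difficulty there; the issue is confined to small subgroups with few deaths.

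**Formulas.**
- Planned interval: d ± [1.96·√(p1q1/n1 + p2q2/n2) + 0.5(1/n1 + 1/n2)], where q = 1 − p.
- Miettinen-Nurminen: the values of d at which the score statistic equals ±1.96, with the variance taken at the constrained maximum-likelihood rates and multiplied by N/(N−1), where N = n1+n2.

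**No deaths in either arm.** The planned half-width is 0.5(1/20 + 1/10) = 7.5 points, or 0.5(1/40 + 1/20) = 3.75 points. The score limits have a closed form here: u/(1−u) = 3.84·N/[(N−1)n], with n = n1 for the upper limit and n = n2 for the lower.
- 20/10, upper: 3.84×30/(29×20) = 0.199, so u = 16.6 points. Lower: 3.84×30/(29×10) = 0.397, so u = 28.4.
- 40/20, upper: 3.84×60/(59×40) = 0.098, so u = 8.9. Lower: 3.84×60/(59×20) = 0.195, so u = 16.3.

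**Comparison (percentage points).**

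| Deaths, test v control | Planned | Width | Miettinen-Nurminen | Width |
|---|---|---|---|---|
| 0/20 v 0/10 | −7.5 to +7.5 | 15.0 | −28.4 to +16.6 | 45.0 |
| 0/40 v 0/20 | −3.75 to +3.75 | 7.5 | −16.3 to +8.9 | 25.2 |
| 2/40 v 0/20 | −5.5 to +15.5 | 21.0 | −11.6 to +16.6 | 28.3 |
| 4/40 v 2/20 | −19.9 to +19.9 | 39.7 | −21.5 to +15.5 | 37.0 |

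The planned bar is about a third of the score width in the first two rows (15.0/45.0 = 0.33; 7.5/25.2 = 0.30) and about three quarters in the third (21.0/28.3 = 0.74). With deaths in both arms it is slightly wider: 7% for 4/40 v 2/20, and 6% for 20/200 v 10/100 (15.9 against 15.0). A 30-subject row with no deaths (±7.5) would therefore look tighter than a 300-subject row with 30 deaths (15.9/2, about ±8.0).

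**How often this could happen.** The chance of no deaths in both arms is (1−p)^N when mortality is p in each.

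| Size | p = 10% | p = 5% | p = 3% |
|---|---|---|---|
| 20/10 (N = 30) | 4% | 21% | 40% |
| 40/20 (N = 60) | 0.2% | 5% | 16% |

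An empty control arm is more common: at 10% mortality, 0.9^10 = 35% with 10 controls and 0.9^20 = 12% with 20.

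**Coverage.** Exact coverage of the planned interval is the sum of the two binomial probabilities over all tables whose interval contains the true difference. It can fall well below 95% in small subgroups with unequal rates: 86.8% at 20/10 with 3% v 15%, 87.7% at 40/20 with 3% v 10%, and 90.0% at 20/10 with 10% v 2% (Miettinen-Nurminen 97.7% in the last case). At 100/50 and above, with rates of 5% to 10%, it is about 96% to 98%.

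**The case against.** The strongest reply is that the plot is descriptive. It carries no margin, alpha or decision rule. The statement that "a non-inferiority margin of 10% will be used" belongs to the primary comparison in SAP 8.1.2.1, whose standard error is protected against empty cells. That stands, and it sets the severity.

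Sparse rows are also plausible rather than shown. The SAP 14 remark is about randomization strata, which cross several factors; it does not say that any single-factor subgroup lacked deaths in both arms. At the planned 10% mortality such a row is unlikely even at 20/10. Rest of World is the best-documented candidate. The eGFR ≥250 mL/min row will be nearly empty because the protocol excludes values above 250, and no interval would tell much there.

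Three stronger readings are tempting but not supported:
- A reader might infer that the interval is too wide wherever deaths do occur. With deaths in one arm it can be too narrow, and with deaths in both the excess was only 6% to 7% in the tables above.
- A reader might infer that a row without deaths would falsely rule out a 10-point excess. That holds near 20/10, where the score upper limit is +16.6. At 40/20 the score interval itself stops at +8.9.
- A reader might infer that every later subgroup section must use the same interval. The cross-references are mainly to the subgroups and do not expressly name the interval.

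The score method is not perfect either: at 40/20 with 5% v 10% its coverage is 93.7%, against 94.3% for the planned interval. Finally, the sponsor may have meant to carry over the (m+0.5)/(n+1) device. Without a continuity term, that would give a half-width of 7.7 points at 0/40 v 0/20, a width of 15.3, still narrower than 25.2. The SAP would then need to say so.

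**Conclusion.** The point holds as a minor one. The interval planned in SAP 8.1.2.4 understates uncertainty when one or both arms of a subgroup have no deaths. In the assumed tables its width is about 0.3 of the score width with no deaths at all and about 0.74 with deaths in one arm only. In small subgroups with unequal rates its coverage can drop to about 87%.

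This rests on the usual correction 0.5(1/n1+1/n2) and on assumed subgroup sizes and rates. The documents do not establish that such rows occurred, only that they are plausible. The consequence is a misleading bar on a descriptive plot. It does not touch the non-inferiority conclusion, the power or the sample size.

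**What to change.** In SAP 8.1.2.4, replace the interval with the unstratified Miettinen-Nurminen (score) 95% confidence interval for the risk difference. State that the same interval applies wherever later subgroup sections follow 8.1.2.4.

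The cost is one phrase in the SAP and one program option, with no new data. Intervals become asymmetric about the point estimate, which a footnote can explain. If the SAP is already final, SAP 1 provides for documenting later changes in the clinical study report. This is a free improvement.
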